#### M Period only:

The primary analysis described above will be repeated using data from the Maintenance period only as response. For subjects who did not reach the Maintenance period, their Transition period data will be used to represent their M period data.

A similar ANCOVA model will be used, and if distributional assumptions are not met, a nonparametric analysis will be performed.

Treatment by baseline seizure category interaction: The primary analysis described above will be repeated with baseline seizure frequency as a categorical variable, rather than a covariate. Baseline seizure frequency per 28 days will be categorized as either < 10; 10-50; or >50.

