**Taper Period:**

Subjects who complete the Maintenance Period and will not be continuing into the open-label extension study and subjects who discontinue from the study early will be tapered off from study medication. Study medication will be administered as equal doses BID in the morning and in the evening approximately 12 hours apart, with food. Each dose should be separated by a minimum of 8 hours and a maximum of 12 hours. A missed dose of study medication may be taken later up to 8 hours before the next scheduled dose; otherwise, the missed dose should not be given. IMP will be administered using the oral dosing syringe provided.

In order to maintain the blind across all dose groups, all subjects who do not continue into the open-extension study will participate in a dose-tapering procedure over the course of 8 days. On the first day of the tapering period subjects in the ZX008 0.8 mg/kg/day group will decrease to a dose of

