**STATISTICAL ANALYSIS PLAN**  
Zogenix International Limited  
ZX008 Study 1

ZX008 0.4 mg/kg/day BID (maximum 30mg/day). After 4 days at this dose level (Day 5), subjects randomized to the ZX008 0.8 mg/kg/day group will decrease their dose to 0.2 mg/kg/day. Subjects in the ZX008 0.2 mg/kg/day group will decrease their dose to placebo on the first day of tapering while doses in the placebo group will remain constant throughout the tapering procedure. On Day 9, all subjects will stop taking study medication. The taper is expected to take a total of 8 days (Table 3). A new bottle of IMP will be started by the subject at each level of the taper step.

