**Transition Period:**

Subjects who complete the Maintenance Period and will be continuing into the open-label extension study will be transitioned from double-blind study medication to open-label ZX008 (Table 4). Study medication will be administered as equal doses BID in the morning and in the evening approximately 12 hours apart, with food. Each dose should be separated by a minimum of 8 hours and a maximum of 12 hours. A missed dose of study medication may be taken later up to 8 hours before the next scheduled dose; otherwise, the missed dose should not be given. Study medication will be administered using the oral dosing syringe provided.

All subjects entering the open-label extension study will be transitioned from their blinded daily dose (placebo, 0.2 mg/kg/day, 0.8 mg/kg/day, or 30 mg/day) to the 0.2 mg/kg dose during the 2-week interval between Visits 12 and 13, without breaking the blind. The IVR/IWR system will assign two bottles of IMP to the subject, one for each step in the transition. A new bottle of IMP will be started by the subject at each level of the transition step.

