**Table 4. Transition Algorithm**

Dose Group in Double-Blind Study	Transition Step 1 Day 1-4 after Visit 12	Transition Step 2 Days 5-14 after Visit 12
ZX008 0.2 mg/kg/day	ZX008 0.2 mg/kg/day	ZX008 0.2 mg/kg/day
ZX008 0.8 mg/kg/day	ZX008 0.4 mg/kg/day	ZX008 0.2 mg/kg/day
Placebo	ZX008 0.2 mg/kg/day	ZX008 0.2 mg/kg/day

Note: maximum daily dose of ZX008 is 30 mg.

Subjects who had been randomized to placebo increase their dose to 0.2 mg/kg/day beginning on Day 1 of the transition (the day following Visit 12.) Subjects who had been randomized to 0.2 mg/kg/day will continue to receive that dose. Subjects who had been randomized to 0.8 mg/kg/day or were receiving the maximum dose of 30 mg/day decrease to a dose of ZX008 0.4 mg/kg/day, or a

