**STATISTICAL ANALYSIS PLAN**  
Zogenix International Limited  
ZX008 Study 1

---

maximum of 30 mg/day. After 4 days at this dose level (Day 5), these subjects will decrease their dose to 0.2 mg/kg/day. Subjects will report to the clinic on Day 15 for enrollment into the open-label extension study.

Data from the Taper or Transition period will not be included towards the planned efficacy endpoints except where specified, but will be included in the safety analyses.

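### The Maintenance-only repeat of the seizure-frequency analyses relies on Transition data that subjects who never reached Maintenance do not have

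*SAP*

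**What the plan says.** The Study 1 SAP (6.3.1.1, M Period only) and the Study 2 SAP (8.1) repeat the primary ANCOVA with Maintenance-period seizure frequency as the response. In identical words, both add: "For subjects who did not reach the Maintenance period, their Transition period data will be used to represent their M period data". The comparison of 0.2 mg/kg/day with placebo inherits this, because Study 1 SAP 6.3.2.1 and Study 2 SAP 8.2.1 apply the primary methods to it and repeat it for Maintenance.

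The periods are defined in Study 1 SAP 3.3 and Study 2 SAP 2.7. On Transition, Study 1 says: "Subjects who complete the Maintenance Period and will be continuing into the open-label extension study will be transitioned". On Taper, it says: "subjects who discontinue from the study early will be tapered off from study medication". Study 2 has the same rules in the past tense. Section 3.3 also states: "Data from the Taper or Transition period will not be included towards the planned efficacy endpoints except where specified". Study 1 SAP 6.1.7 allows no imputation for efficacy endpoints. The period tables (Study 1 SAP 6.1.6, Study 2 SAP 6.5) put Taper and Transition into one two-week window, which may start from an early termination visit.

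**The concern.** The rule names a group of subjects and a data source that do not meet. A subject who stops before Maintenance tapers and never enters Transition. The programmer is left either to substitute nothing or to take whatever diary data follow the termination visit. The first choice shrinks an analysis that the plan places on mITT. The second scores days off the randomised dose as Maintenance days. Neither gives the comparison that a Maintenance-only analysis is meant to give, and the plan does not say which is intended.

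**Working it through.** There is no stated figure to reproduce for the rule itself, so the check sets the definitions side by side and then sizes each reading.

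**1. Can the named subjects have Transition data?** Transition requires completing Maintenance; the rule applies to subjects who did not start it. The two sets do not overlap, so strictly nothing is substituted.

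**2. Are such subjects in the analysis set?** mITT needs one dose and one week of diary data (Study 1 SAP 5.4, Study 2 SAP 5.3). Titration runs 14 ± 4 days. A subject who leaves in the second week can be in mITT with no Maintenance diary days. The per-protocol set requires at least 4 weeks of Maintenance, so the per-protocol repeat is not affected.

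**3. What would the merged window supply?** For an early terminator it holds Taper data. On the low dose the plan says: "Subjects in the ZX008 0.2 mg/kg/day group will decrease their dose to placebo on the first day of tapering". The Taper table gives the 0.8 mg/kg/day arm 0.4 on Days 1-4, 0.2 on Days 5-8, and nothing from Day 9. Nominal mean daily doses in mg/kg/day over 14 days, ignoring the 30 mg/day cap, are:

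| Arm | Merged window, early terminator | Full Titration |
|---|---|---|
| Placebo | 0 | 0 |
| 0.2 | 0 | 0.2 |
| 0.8 | (4×0.4 + 4×0.2 + 6×0)/14 = 2.4/14 = 0.171 | (4×0.2 + 4×0.4 + 6×0.8)/14 = 7.2/14 = 0.514 |

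In the merged window the dose contrast with placebo falls from 0.2 to 0 for the low dose and from 0.8 to 0.171 for the high dose. These figures start the window the day after Visit 12, as in Study 1. The Study 2 text prints a start 4 days after Visit 12, which would lower the high-dose mean to (1×0.4 + 4×0.2)/14 = 0.086.

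**4. How many subjects?** Study 2 SAP 6.4 gives 9 dropouts of 119 in Study 1: 9/119 = 7.56%, which reproduces. The split between Titration and Maintenance is not given, so the range is 0 to 9. No count is given for Study 2.

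**5. How far does the rule reach?** It is stated for the primary variable and carries to the 0.2 mg/kg/day seizure-frequency comparison. It is not stated for the responder or longest-interval endpoints. That is 2 of the 6 tests in the hierarchy, and only in their Maintenance-only repeats.

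**6. Which word was probably meant?** The period tables already tabulate safety data for subjects who withdraw before Maintenance treatment under Titration. The adverse event sections (Study 1 SAP 6.4.1, Study 2 SAP 10.3) name a titration/transition period ending at Visit 13, where taper/transition fits. So the terms are confused elsewhere too, and Titration is the period these subjects actually have.

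**The case against.** The strongest reply is that little hangs on this. The testing hierarchy has no Maintenance-only step, and both SAPs make the log-scale mITT analysis the main criterion for efficacy. Titration dropouts remain in the primary analysis, and Study 2 adds two dropout sensitivity analyses. A loss of subjects would show, because the number of observations for Maintenance is a required descriptive statistic. All of this stands, and it limits the weight of the point. It does not make the rule workable.

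A reader might infer that placebo subjects would be counted in Maintenance while taking active drug, since the plan says of Transition: "Subjects who had been randomized to placebo increase their dose to 0.2 mg/kg/day beginning on Day 1 of the transition". In that window the nominal means are 0.20, 0.20 and (4×0.4 + 10×0.2)/14 = 0.257 mg/kg/day for placebo, low and high dose, which nearly removes the contrast. But only Maintenance completers enter Transition, and the rule does not touch them. A placebo subject who leaves early tapers on placebo, so this harm does not reach the subjects named.

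A reader might also infer that all six hierarchy tests are affected when repeated for Maintenance. The text supports two.

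It is also fair to say that the documents do not prove Titration was intended; the merged Taper/Transition label is a rival reading. Nor would Titration data put everyone on the randomised dose: a 0.8 mg/kg/day subject who leaves by Day 8 has taken only 0.2 and 0.4 mg/kg/day.

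**Conclusion.** The substitution rule fails as written in both SAPs. It is void under the strict reading, and under the merged-window reading it supplies off-dose data for the active arms only. It affects the Maintenance-only repeats of the two seizure-frequency comparisons, in 0 to 9 of 119 Study 1 subjects and an unstated number in Study 2. The primary Titration plus Maintenance result and the Type 1 error control do not depend on it. It should be fixed as a defect in a planned supportive analysis; it is no threat to the main conclusion. The contradiction rests only on the plan's definitions of Transition and Taper. The upper bound of 9 assumes that every Study 1 dropout left before Maintenance, which is the extreme case.

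**What to change.** In Study 1 SAP 6.3.1.1 and Study 2 SAP 8.1, reconcile the sentence with the Taper, Transition and period-window definitions by naming Titration-period data as the substitute. Note that in the 0.8 mg/kg/day arm these data are partly below the target dose. State that no Taper or Transition diary data enter the Maintenance-only efficacy analyses, which closes the exception left open in Study 1 SAP 3.3 and Study 2 SAP 2.7. In Study 1, also square the substitution with the no-imputation statement in 6.1.7. Say whether the rule extends to the responder and longest-interval repeats, and report by arm how many subjects it applies to.

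The cost is a few sentences and one derivation step in each SAP, with no new data. Study 2 SAP 2.3 says that Study 1 was reported in September 2017, so any change to Study 1 output must be labelled a correction or post hoc.

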#### **6.3.1.2 Supplementary and Sensitivity Analyses**

##### **Impact of AED Medications**

Subjects in the study are required to be on stable background therapy. An additional analysis will be performed to assess the impact on the primary analysis of changes in dose or type of concomitant AED medications, which are protocol violations, that may occur during the course of the study. Specifically, the percentage of subjects who had a change in dose or type of concomitant AED medication will be compared between treatments. For this analysis, each subject will be classified according to whether the subject had a change in the prescribed dose or type of concomitant AED medication during the T+M period. Fisher's exact tests will be used to compare the active dose group with the placebo group.

##### **Per protocol Analysis**

Additionally, the primary efficacy analysis will be repeated on the per protocol population (which excludes subjects with important protocol deviations that may affect the inference on efficacy such as a change in dose or type of concomitant AED medication).

---

### Percentage Reduction from Baseline

The ANCOVA employed in the primary analysis uses  $\log \text{CSF}_{T+M}$  as the response adjusts for baseline seizure frequency by incorporating  $\text{CSF}_B$  as a factor in the model. The alternative approach described here calculates the percentage change in CSF from baseline directly and uses that quantity as the response variable in an ANCOVA model. Specifically, the ANCOVA will use the percentage change from the T+M period to baseline as the response variable, baseline CSF as a covariate, and treatment and age stratum as classification factors. The analyses will be repeated for the M period only using the baseline as covariate.

If the distributional assumptions for the parametric analysis are not met, a nonparametric ANCOVA will be used for the ranks of the dependent variable as response, using the ranks of the baseline as covariate.

### Criteria for Establishing Efficacy

While several supportive and/or supplementary analyses are specified above, the main criterion for demonstrating efficacy will be the primary analysis using the log transform for the mITT population. It is conceivable that some or all of these supplemental analyses may not reach statistical significance. However, it is expected that the direction of effect will be in favor of the test treatment. As an example, a statistically significantly smaller least squares adjusted MCSF for the treatment group compared to placebo, in the presence of a smaller proportion of subjects on 0.8 mg/kg than Placebo subjects increasing their dose of concomitant AEDs will be strong evidence for efficacy of the experimental treatment.

### 6.3.2 Key Secondary Analysis

#### 6.3.2.1 MCSF for ZX008 0.2 mg/kg/day versus Placebo

The MCSF during the T+M period will be analyzed and compared between the ZX008 0.2 mg/kg/day group and the placebo group using the same methods employed for the primary analysis. Following the same strategy as the ZX008 0.8 mg/kg/day comparison, a nonparametric analysis using ranks will be used for the ZX008 0.2 mg/kg/day comparison if the assumptions of the parametric ANCOVA model are not met.

The analysis will be repeated for the M period.

Similar supplementary analyses will be performed as for the comparison of the 0.8 mg/kg group with placebo.

#### 6.3.2.2 Proportion with $\geq 50\%$ Reduction from Baseline in Convulsive Seizure Frequency

Subjects with a percent reduction in convulsive seizures of at least 50 percentage points from baseline will be identified and the overall proportion within each treatment tabulated. That is, the proportion of subjects in the ZX008 0.8 mg/kg/day group who have a decrease in convulsive frequency of at least -50 percentage points will be compared to the analogous proportion in the placebo group.

Similarly, the proportion of subjects in the ZX008 0.2 mg/kg/day group who have a change in convulsive frequency of at least -50 percentage points will be compared to the analogous proportion in the placebo group.

The comparison between treatment groups will be made using a logistic regression model that incorporates the same factors as the ANCOVA used in the primary analysis. This will model a categorical response variable (achieved 50 percentage point reduction, yes or no) as a function of treatment group (ZX008 and placebo) and age group (< 6 years, ≥6 years).

Raw descriptive statistics will be presented by treatment group, and will include the number and proportion of subjects < 6 years, ≥6 years, and overall achieving the reduction along with the model estimated odds ratio (including a 95% confidence interval) and p-value for comparison of ZX008 0.8mg/kg/day to placebo and ZX008 0.2mg/kg/day to placebo separately.

### 6.3.2.3 Longest Interval between Convulsive Seizures

The longest interval between convulsive seizures will be analyzed.

For each subject, the longest interval between convulsive seizures will be calculated over the entire T+M period. This will be derived as the maximum of the number of days between consecutive convulsive seizures. The intervals between consecutive convulsive seizures will be calculated as below, after which the longest interval between convulsive seizures will be derived.

If a subject has two consecutive days of missing diary data, the current seizure-free interval will be ended on the first date of missing diary data, and a new one begun on the next date that diary data are available and no seizure occurs. [In that case, for purpose of calculation of this variable, all intervening days, after the 2nd day, with missing diary data, will be assumed to have a convulsive seizure occurrence, until the first available date with non missing diary data.]

Let Date0 (=Day1) be the first day of treatment. If convulsive seizure occurs on five days having dates as Date1, Date2, Date3, Date4 and Date5, where  $Date5 > Date4 > Date3 > Date2 > Date1 \geq Date0$ , and let LDT = Last date of treatment in the maintenance period, where  $LDT \geq Date5$ , then the time interval between convulsive seizures will be calculated as follows:

$$I1 = Date2 - Date1$$

$$I2 = Date3 - Date2$$

$$I3 = Date4 - Date3,$$

$$I4 = Date5 - Date4.$$

For completeness, we calculate the time to the first seizure as

$$I0 = Date1 - Date0,$$

and the time from the last seizure to end of treatment as

$$I5 = LDT - Date5.$$

Here the duration of the longest interval = Maximum (I0, I1, I2, I3, I4, I5).

If the subject does not experience a seizure during treatment, then the last available diary date will be used to compute the duration of the longest interval as follows:

The longest interval=last available diary date – Date0

The median time of the longest convulsive seizure-free interval will be presented. Additional summary statistics will be presented, including mean, minimum, maximum, the 25th and 75th percentiles, 95% confidence intervals on the difference in medians between groups (Hodges-Lehman estimator).

The Wilcoxon rank sum test will be used to test for differences between each treatment arm and placebo, and the p-value from this test will be presented. A histogram presenting the percentage of subjects whose longest seizure free interval is <10, 11-20, 21-40, 41-60, 61-84, and ≥84 days will accompany all descriptive statistics and all data will be provided in a data listing.

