### 6.3.1 Primary Efficacy Analysis

The primary efficacy endpoint is the change in the mean convulsive seizure frequency (MCSF) per 28 days between the Baseline and T+M periods. For each subject, the CSF will be calculated from all available data collected during the Baseline and T+M Periods, and the treatment group mean convulsive seizure frequency per 28 days (MCSF) will be calculated for the baseline and T+M period.

The baseline period is the 42 days immediately preceding the Randomization visit and the T+M period is planned for 14 weeks. However, actual durations will be computed for each subject based on the individual subject's start and stop dates for each period, except that if the baseline period is longer than 42 days, the average for the baseline period will be taken over the 42 days immediately preceding the Randomization visit.

The convulsive seizure frequency will be counted from the daily diary records provided by the Subject or Parent/Caregiver.

For any individual subject, the convulsive seizure frequency per 28 days during the baseline period (CSFB) will be derived as follows:

$$CSF_B = \frac{28 \times \text{Total number of convulsive seizures during the Baseline Period}}{\text{Total number of days in the Baseline Period with nonmissing diary data}}$$

For each treatment group, the mean is obtained by averaging over the subjects in the treatment group.

Similarly, for each subject, the convulsive seizure frequency per 28 days for the T+M period ( $MCSF_{T+M}$ ) is derived as below:

$$CSF_{T+M} = \frac{28 \times \text{Total number of convulsive seizures in the T + M period}}{\text{Total number of days in the T + M period with nonmissing diary data}}$$

The percentage change from baseline for any individual subject will be estimated by

$$(CSF_{T+M} - CSF_B) * 100 / CSF_B$$

The difference from baseline will be estimated by  $CSF_{T+M} - CSF_B$ .

Corresponding treatment group means are designated with “M” preceding the quantity. For each treatment group, descriptive statistics for MCSF during baseline, T+M and M only, as well as the differences and % changes from baseline, will include the number of observations, mean, standard deviation, median, minimum and maximum, overall and by age group (<6 years, ≥6 years).

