intervals is informative about the underlying distribution, as subjects at a higher risk of experiencing recurrent events are likely to have shorter and hence more seizure-free intervals during the 84 day treatment period. Thus, a simple analysis comparing medians of the largest seizure free intervals was proposed.

- Responder analyses – Protocols 1501 and 1502 include a  $\geq 40\%$  response analysis as one of the key secondary endpoints. It was decided to not include this endpoint.
- An analysis of the percentage of subjects who achieve a 25% reduction in seizures was added. The number of subjects whose seizures worsen during the study will be included, along with the percentage of worsening.
- The Protocol states that the BRIEF rating scale will be used to evaluate cognition in children aged 2-18. The BRIEF-P will be used for children aged 2-4, and the BRIEF will evaluate children aged 5-18.
- Interim analysis – Protocols 1501 and 1502 do not delineate an interim analysis. However, this Study 1 Analysis Plan is a pooled analysis of data from the first 120 subjects to be randomized into studies 1501 and 1502, in order to assess the benefit and risk at an earlier timepoint than fully recruiting each trial independently. Both studies will continue to enroll, and the remaining approximately 120 subjects will be analyzed as Study 2, under a separate analysis plan.

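### Longest convulsive seizure-free interval: the Hodges-Lehmann CI is mislabelled as a difference in medians, and the Study 1 histogram bins miss 10 days and count 84 days twice (minor)

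*SAP*

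**What the plan says.** Section 6.3.2.3 of the Study 1 SAP defines the endpoint in whole days: "This will be derived as the maximum of the number of days between consecutive convulsive seizures". The intervals are differences between calendar dates.

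Three kinds of output follow:

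- **Group summaries.** "The median time of the longest convulsive seizure-free interval will be presented", together with the mean, range and quartiles.
- **Effect size.** The section calls for "95% confidence intervals on the difference in medians between groups (Hodges-Lehman estimator"). It states no location-shift assumption.
- **Test and figure.** "The Wilcoxon rank sum test will be used to test for differences between each treatment arm and placebo". A histogram is to show the percentage of subjects whose "longest seizure free interval is <10, 11-20, 21-40, 41-60, 61-84, and ≥84 days". Appendix 1 lists it as Figure 14.2.3.2 (mITT).

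Section 6.9, explaining why the log-rank test was dropped, says that "a simple analysis comparing medians of the largest seizure free intervals was proposed". The reference to medians is therefore not an isolated phrase.

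Section 8.2.1 of the Study 2 SAP carries the same interval label and the same bins. Its output index (Section 15), however, lists Figures 14.2.3.2 and 14.2.3.4 as boxplots and has no histogram for this endpoint.

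**The concern.** The label names one quantity and the method estimates another. The two-sample Hodges-Lehmann estimate is the median of all active-minus-placebo differences. It generally coincides with the difference of the two medians only when one distribution is the other moved by a constant. A longest gap between seizures cannot exceed the observation period ("the T+M period is planned for 14 weeks") and responds to treatment through the seizure rate, so its spread and shape would be expected to change as well as its location. Because the group medians are also presented, a reader can subtract them and get a number that disagrees with the one labelled as their difference.

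The bins are a separate slip. A program that follows them literally omits some children from a planned figure and may count others twice.

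At stake are the wording of the effect size for a key secondary endpoint and the accuracy of one descriptive figure.

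**Working it through.** The plan gives no numerical figure for this endpoint, so there is nothing of its own to reproduce. The bin check needs no assumptions. The estimator check does.

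**1. Bins.** Inputs: whole-day values and the printed edges "<10, 11-20, 21-40, 41-60, 61-84, and ≥84 days". Every value from 0 to 103 days was compared with the six bins.

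| Value (days) | Bins containing it |
|---|---|
| 10 | none (the lowest bin stops at 9, the next starts at 11) |
| 84 | two (61-84 and ≥84) |
| every other value, 0 to 103 | exactly one |

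**2. Two quantities.** Write A for active and P for placebo.

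- Difference in medians: median(A) − median(P).
- Hodges-Lehmann: median of all A_i − P_j.

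Under a pure 12-day shift both equal 12.0. To see the effect of skewness and the cap, whole-day lognormal values were capped at 98 days (14 weeks × 7). Placebo was assumed to have median 10 and log-SD 0.7. None of these distributions comes from the documents.

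| Assumed active arm (median, log-SD) | Difference in medians | Hodges-Lehmann | Gap |
|---|---|---|---|
| 25, 0.7 | 15 | 14 | 1 |
| 25, 1.0 | 15 | 14 | 1 |
| 30, 1.0 | 20 | 18 | 2 |
| 20, 1.2 | 9 | 8 | 1 |

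A day-level simulation using the plan's own interval formulas over 98 days gave a similar picture. It assumed a median baseline of 15 to 25 convulsive seizures per 28 days, log-SD 1.0 to 1.2, and an active rate ratio of 0.15 to 0.4 with varying response. Four scenarios gave differences in medians of 7, 9, 15 and 6 days against Hodges-Lehmann values of 6, 7, 13 and 4. The gaps were again 1 to 2 days.

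**3. Coverage at 40 per arm.** There are 40 × 40 = 1,600 pairwise differences. The rank-based 95% limits are the k-th smallest and k-th largest, with

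k = floor(1,600/2 − 1.96 × √(1,600 × 81/12)) = floor(800 − 1.96 × 103.9) = 596.

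Over 4,000 replicates of the capped lognormal model with active median 25:

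| Active log-SD | Difference in medians | Hodges-Lehmann | Coverage of difference in medians | Coverage of Hodges-Lehmann shift |
|---|---|---|---|---|
| 1.0 | 15.1 | 13.8 | 92.0% | 93.0% |
| 0.7 | 15.0 | 13.8 | 92.4% | 94.0% |

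The day-level simulation put coverage of the difference in medians at 91% to 95%. In the table, coverage of the interval's own target is also below 95%. Only about 1 to 2 percentage points of the shortfall therefore come from aiming at the wrong quantity.

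**4. How many children the bins touch.** Under the day-level assumptions, exactly 10 days occurred in about 3.6% to 7% of placebo children: 40 × 0.036 = 1.4 to 40 × 0.07 = 2.8, so roughly one to three of 40. Exactly 84 days occurred in 0.3% or less: 120 × 0.003 = 0.36, less than one child expected in the whole study.

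**The case against.** The defence is largely right about consequence. The estimator is named in the same phrase as the label, so a programmer knows what to compute, and it is the natural companion to the Wilcoxon test. The bin edges look like a slip that programming would expose, and the plan also promises all data in a listing. The numerical gap is small and depends on assumed distributions. All of this stands and keeps the point minor. It does not make the label correct or the bins usable as printed.

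Four stronger readings are tempting, and the documents do not support them:

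- **The gatekeeping is compromised.** Steps 3 and 6 in Section 6.1.2 turn on significance at 0.05, and the test is the Wilcoxon. Neither the interval label nor the histogram enters the hierarchy.
- **The endpoint's summaries are wrong as a whole.** The medians, means, quartiles, ranges and p-values are unaffected.
- **A value of 84 days marks a child with no convulsive seizure in Maintenance.** Section 6.1.6 of the Study 1 SAP runs Titration through Visit 6 and Maintenance from the next day through Visit 12. Nominally 99 − 15 = 84, but each visit has a window of ±4 days, so 84 is not a fixed marker and the plan gives it no such meaning.
- **Large disagreements in single trials measure the mislabelling.** In larger-effect scenarios the estimate differed from the subtracted sample medians by 3 days or more in 12% to 30% of simulated 40-per-arm trials. That figure also contains ordinary sampling disagreement between two estimators.

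**Conclusion.** Two descriptive outputs are wrong as written. The confidence interval is attached to a quantity that the named method does not in general estimate. The Study 1 histogram bins are neither exhaustive nor mutually exclusive.

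The bin fault is certain, since it follows from the printed edges and a whole-day endpoint. Percentages fail to total 100% only if a child's value is exactly 10 or 84, and any clustering of placebo children near 10 days is an assumption.

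The label fault is certain in principle and modest in size: about 1 to 2 days, with coverage of the difference in medians around 91% to 95%, under distributions that the documents do not supply. In Study 2 the histogram problem is chiefly a conflict between text and output index. Severity is minor, and no inferential result changes.

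**What to change.** - **Interval label (Study 1 SAP 6.3.2.3; Study 2 SAP 8.2.1).** Call it *Hodges-Lehmann location shift (median of all pairwise ZX008-minus-placebo differences) with 95% CI*. If a difference in medians is what is wanted, keep that label and use a bootstrap interval for that quantity.
- **Study 1 bins.** Make them contiguous, for example ≤10, 11-20, 21-40, 41-60, 61-83 and ≥84 days. Each whole-day value then falls in exactly one bin.
- **Study 2.** Either delete the histogram sentence and rely on the indexed boxplots, or correct the bins and add the histogram to the index.

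The cost is a few words in each SAP and one format statement in the program. A bootstrap interval, if chosen, adds a short piece of code. No new data are needed and the Wilcoxon test stays as planned. The only drawback is a less familiar label.
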